- 6) Patients whose Mini-Mental State Examination (MMSE) scores were less than 24.
- 7) Patients who had medical history that did not fit to exercise, such as orthopedics diseases or cardiopulmonary dysfunction.
- 8) Patients who received education less than 6 years.
- 9) Patients who could not walk and live independently.
- 10) Patients who received brain surgery (e.g. deep brain stimulation);
- 11) Patients whose exercise length longer than 50 minutes per week.

All participants were fully informed and signed written consent forms. This study was approved by the ethic committee of Ruijin Hospital affiliated to Shanghai Jiao Tong University School of Medicine.

2. Randomization, Blinding and Follow-Up

There was no randomization adopted. Assessments were done at baseline and the three follow-ups (Nov. – Dec. 2019, Oct. - Nov. 2020 and Jun. – July 2021). We also monitored the frequency and lengths of Tai Chi exercise for each patient. Patients whose training were less than 60 minutes per time or less than twice per week were regarded as giving up training. The flow chart of recruitment and follow up was shown in Part II.

PD patients who did not receive Tai Chi training were matched to Tai Chi training PD patients with similar age, sex, disease duration and initial Hoehn - Yahr staging by propensity score matching methods. They also received evaluation at baseline and three follow-ups (Nov. – Dec. 2019, Oct. - Nov. 2020 and Jun. – July 2021).

Since this is an interventional study of movement, we cannot perform the blinding on patients. Thus, the assessors and the statisticians were blinded to study design. The ethic committee monitored the whole process of blinding. Patients were demanded not to tell their group assignments to the assessors.

3. Exercise Interventions and Quality Control

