5.1 Primary Outcome

The primary outcome was the annual change of UPDRS total score measured in “ON” state at three follow-ups.

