5.2 Secondary Outcomes

The secondary outcomes were annual change of the following indicators except the need of increasing antiparkinsonian therapies which were analyzed by survival analysis:

- (1) the change of LEDD⁴
- (2) the need of increasing antiparkinsonian therapies, including both the need of increasing antiparkinsonian drugs and the need of surgery, such as DBS or lesion surgery.
- (3) Motor evaluations: UPDRS part III as overall motor evaluations; TUG and BBS.
- (4) Other non-motor symptoms, including autonomic function, mood, sleep and cognition, assessed by rating scales.
- (5) Quality of life: PDQ-39;
- (6) the difference of prevalence of complications (dyskinesia, on-off phenomenon, dystonia, PD-MCI, hallucinations, restless legs syndrome).

NOTE: We consider the following aspects as the evidences for delaying disease progression:

- (1) the annual change of UPDRS total score;
- (2) the annual change of LEDD;
- (3) the need of increasing antiparkinsonian therapies.

6. Statistical Analysis

R (version 3.5.1) and RStudio (version 1.1463) were used to perform statistical analysis.

Packages stats (version 3.5.1), base (version 3.5.1), spinds (version 2.2.0), lars (version 1.2), nlme (version 3.1-145), plyr (version 1.8.5), PGEE (version 1.5), ggplot2 (version 3.2.1), survival (version 2.43-3) and survminer (version 0.4.3) were introduced into statistical analysis. Figures were plotted in Prism 9 (version 9.3.1, San Diego, CA).

All analysis about primary and secondary outcomes were conducted on an intention-to-treat basis. Analysis of variance (ANOVA) were used in comparing at numerical demographic information. Pearson Chisq-Square test or Fisher test were used in analysis at categorical demographic information. Shapiro-Wilk normality test was used to assess the normality of variables. Independent-sample t-tests (with 95% confidence intervals) were used to compare group means. Data were presented in the way of between-group differences. The longitudinal effects of self-changes were calculated using repeated measures ANOVA.

We built a cohort which started enrollment since 2016, then more patients were enrolled gradually into another 4 classes (2nd Class: start from Nov. 2016; 3rd Class: start from Mar. 2017; 4th Class: start from Sept. 2017; 5th Class: start from Jan. 2018). All the patients in those 5 classes were trained continually and has been received assessment in the follow-up of 2019, the follow-up of 2020 and the follow-up of 2021.

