We set the rate of UPDRS total score change (per year) as the primary outcome. As for the secondary outcomes, UPDRS part III, other motor evaluations (TUG and BBS), evaluations of non-motor symptoms (autonomic function, mood, sleep, and cognition, assessed by rating scales), quality of life evaluated by PDQ-39, the change of LEDD, and the difference of prevalence of complications (dyskinesia, on-off phenomenon, dystonia, PD-MCI, hallucinations, restless legs syndrome). We also observed the need for increasing antiparkinsonian therapy, including increasing antiparkinsonian drugs, and deep brain stimulation (DBS). LEDD of patients who received DBS were not taken into account.

We make the comparisons between the patients who received Tai Chi training and patients who did not receive Tai Chi training as controls. Analyses of the adjusted means of change from baseline to each follow-up in rating scales were done with logarithmic linear model of covariance that included the following fixed effects: treatment group

(Tai Chi = 1, control group = 0), months in this trial, the changed amount of LEDD and baseline Hoehn-Yahr score. Years of education were also included when analyzing PDCRS. We calculated the *p* value with the bootstrap method for resampling 1000 times. To demonstrate the results, mean change with its 95% confidential intervals (CIs) was introduced. Kaplan Meier plot with table of number at risk was introduced. Bonferroni correction was introduced.

7. Safety Reporting: Adverse events (AEs) and serious adverse events (SAEs)

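### The between-group analysis does not say whether the three follow-ups are fitted together or separately, how within-patient correlation is handled, or what the bootstrap resamples

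*Combined protocol and SAP*

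**What the plan says.** - **Data structure.** Section 2: "Assessments were done at baseline and the three follow-ups (Nov. – Dec. 2019, Oct. - Nov. 2020 and Jun. – July 2021". Each patient can therefore contribute up to three changes, all measured from the same baseline score.
- **Primary outcome.** Section 5.1: "The primary outcome was the annual change of UPDRS total score measured in “ON” state at three follow-ups". No single follow-up is named as primary.
- **Between-group model.** Section 6: "Analyses of the adjusted means of change from baseline to each follow-up in rating scales were done with logarithmic linear model of covariance that included" fixed effects for treatment group, "months in this trial, the changed amount of LEDD and baseline Hoehn-Yahr score". Education is added for PDCRS. No visit factor, group-by-time term, patient effect or within-patient covariance is named.
- **Inference.** "We calculated the *p* value with the bootstrap method for resampling 1000 times". The resampling unit is not given. A Bonferroni correction is announced in the same paragraph, without the family of tests that it covers.
- **Repeated measures elsewhere.** "The longitudinal effects of self-changes were calculated using repeated measures ANOVA". This concerns change within patients, not the contrast between groups.
- **Software.** nlme and PGEE, both usable for correlated data, are in the Section 6 package list. Neither is tied to an analysis.

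**The concern.** Treatment group is constant within a patient. When several positively correlated records per patient are analysed as if independent, the standard error of the group effect is too small. A bootstrap that resamples single records keeps the same assumption, so it does not repair this. The primary outcome is also the first of the three items that Section 5.2 counts as evidence of delayed progression, so the validity of its p value and interval matters.

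The Section 6 text allows two readings:

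- **(a) One fit across follow-ups**, with months as the time covariate. Without a patient term or whole-patient resampling, the errors are too small.
- **(b) A separate fit at each follow-up.** Each patient then gives one record per fit and this problem does not arise. An outcome defined as a rate per year is, however, split over three tests, and nothing says which one decides.

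The months term does not settle the choice. Class starts are staggered, so months in the trial vary between patients even within one calendar follow-up.

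**Working it through.** The plan gives no sample size, alpha or within-patient correlation, so there is no stated figure to reproduce.

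**Inputs.** Follow-ups per patient: m = 3 (Section 2). Assumed: two-sided alpha 0.05 (the plan uses 95% intervals), and correlation ρ between a patient's changes, shown over a range.

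**Why ρ = 0.5 is a natural reference.** Let the four raw scores have equal variance σ² and common correlation r. Then each change has variance 2σ²(1 − r), and two changes from the same baseline have covariance σ²(1 − r). Their correlation is 0.5 whatever r is. Equal variances and equal correlations are both assumptions.

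**Reading (a), rows treated as independent.**

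Design effect DE = 1 + (m − 1)ρ; false-positive rate = 2[1 − Φ(1.96/√DE)].

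At ρ = 0.5: DE = 1 + 2 × 0.5 = 2.0. The naive standard error is 1/√2 = 71% of the true one. 1.96/√2 = 1.386, and 2[1 − Φ(1.386)] = 16.6%.

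| m | ρ | DE | False-positive rate |
|---|---|---|---|
| 3 | 0.2 | 1.4 | 9.8% |
| 3 | 0.3 | 1.6 | 12.1% |
| 3 | 0.5 | 2.0 | 16.6% |
| 3 | 0.7 | 2.4 | 20.6% |
| 3 | 0.9 | 2.8 | 24.1% |
| 2.5 (mean) | 0.5 | 1.75 | 13.8% |
| 2 (mean) | 0.5 | 1.5 | 11.0% |

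Dividing each change by years since class start does not remove the effect. With the class dates (first class taken as January 2016), mid-window follow-ups and equal class sizes assumed, DE at ρ = 0.5 is 1.93 and the rate is 15.9%.

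**Simulation.** No group effect; assumed 100 patients per group; the same class starts and follow-up times; group, months and Hoehn-Yahr in the model; 200 bootstrap resamples per run. LEDD change and the logarithmic form were left out. The second column lets patients progress at different rates (slope SD 0.3 per year, where the single-visit SD is 1).

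| Analysis | ρ = 0.5 (3000 runs) | Random slopes (1500 runs) |
|---|---|---|
| Stacked, rows resampled | 17.0% | 20.9% |
| Stacked, whole patients resampled | 5.3% | 5.6% |
| One follow-up fitted alone | 5.4% | 5.3% |
| Any of three separate fits, unadjusted | 13.3% | 11.9% |
| Any of three, Bonferroni over three | 5.1% | 3.9% |

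**Reading (b), direct check.** For three normal test statistics with pairwise correlation 0.5, the chance that at least one exceeds 1.96 in absolute value is 12.5%. With the Bonferroni limit of 2.394 (alpha 0.05/3) it is 4.4%.

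**The case against.** A reader might infer that the plan treats visits as independent and bootstraps rows, so that its primary test has a 17% error rate. The documents do not support that, for four reasons.

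1. They are silent on the resampling unit. Silence is not a statement that records were resampled.
2. Change to each follow-up, with no visit factor or interaction in the model, fits three separate analyses at least as well as one stacked analysis. Section 6 also compares group means with independent-sample t-tests, a method for one record per patient.
3. Listing fixed effects does not exclude a random effect or a covariance structure. nlme and PGEE could have supplied one. Equally, nlme may have served only the repeated measures ANOVA, so the package list proves nothing either way.
4. A Bonferroni correction is planned, so an unadjusted 0.05 threshold may not be the one applied.

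All four points stand. They reduce the finding from an error in the plan to an analysis that is not fully specified. They do not close it: one permitted reading is anti-conservative, the other leaves the deciding test unnamed, and the text does not let a reader tell which was used. It is also fair that one longitudinal model is not the only valid remedy. Separate fits with a named primary visit or a stated Bonferroni family would control error too.

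**Conclusion.** The point holds as a gap in specification with conditional consequences.

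- **If visits were stacked and rows treated as independent:** a false-positive rate of about 17% instead of 5% at ρ = 0.5, about 10% to 24% for ρ from 0.2 to 0.9, and about 11% to 14% with an average of 2 to 2.5 visits per patient at ρ = 0.5. This rests on an assumed correlation and on an unadjusted two-sided 0.05. The figures refer to the group term as the plan lists it.
- **If each follow-up was fitted separately:** no inflation in any one test. Across the three, the chance of at least one false positive is about 12-13% unadjusted, or 4-5% if Bonferroni covers them.

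The point concerns correlation within a patient only. Matching and Tai Chi classes are separate matters. It should be resolved because it affects the primary outcome and the rating-scale secondary outcomes analysed in the same way, and because resolving it is cheap.

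**What to change.** In Section 6:

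1. Make the primary UPDRS analysis one longitudinal model over all available follow-ups, with a patient random effect or an unstructured within-patient covariance. nlme, already listed, can fit either.
2. Define a single primary contrast: the between-group difference in annual rate of change (group-by-time). A group main effect on change is not by itself a difference in yearly rate.
3. State that each of the 1000 resamples draws whole patients with all their visits, and take both the p value and the 95% interval from it. This also protects the inference if the chosen covariance is too simple, for example when patients progress at different rates.
4. If separate fits per follow-up are kept instead, name one primary visit or state that the Bonferroni correction covers the three.
5. Treat the rating-scale secondary outcomes in the same way.

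Reported results need re-running as a correction only if visits were stacked as independent. The cost is revised wording and, where needed, a re-analysis of data already collected with software already listed. No new patients or visits are required. The drawback is wider intervals and larger p values wherever rows had been treated as independent.

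### The only covariate-adjusted model for rating-scale change conditions on LEDD change, a post-baseline outcome, so its group coefficient is not in general the total group difference in ON-state change

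*Combined protocol and SAP*

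**What the plan says.** The outcome and its analysis are set out in sections 5 and 6 of the protocol.

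- **Primary outcome.** "We set the rate of UPDRS total score change (per year) as the primary outcome" (section 6). Section 5.1 adds that it is measured in the ON state at three follow-ups.
- **Adjusted model.** "Analyses of the adjusted means of change from baseline to each follow-up in rating scales were done with logarithmic linear model of covariance" (section 6). The fixed effects are treatment group, "months in this trial, the changed amount of LEDD and baseline Hoehn-Yahr score". Years of education are added for PDCRS only, and LEDD change stays in. Mixed-model and GEE packages are listed, but no other adjusted model for the scales is described.
- **Unadjusted comparison.** "Independent-sample t-tests (with 95% confidence intervals) were used to compare group means" (section 6). The groups are not randomised. Controls are chosen to have "similar age, sex, disease duration and initial Hoehn - Yahr staging by propensity score matching methods" (section 2).
- **Status of LEDD change.** It is the first secondary outcome in section 5.2. The note there also lists "the annual change of LEDD" as the second of three pieces of evidence for delayed progression, after the annual UPDRS change.
- **Why LEDD can move.** Section 1 requires stable medication but allows increases during follow-up when severity calls for them.

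The plan does not say whether the adjusted result is meant as the total group difference or as a difference with medication change held fixed.

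**The concern.** A covariate measured after baseline that may depend on group is not an ordinary adjustment variable. By listing LEDD change as an outcome, the plan allows that Tai Chi may alter it. The adjusted model then compares patients with equal LEDD change, which removes from the rating-scale result whatever part of the group difference is associated with medication.

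Two mechanisms pull in different directions. Faster progression may lead to a larger LEDD increase, so LEDD change acts as a marker of progression, and holding it fixed can absorb part of a real difference. A larger dose may also lower the ON-state score, so holding dose fixed can uncover a difference that medication hides. The coefficient mixes the two.

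At stake is what the adjusted figures for UPDRS total, UPDRS III and the other scales mean. They would probably be read as the group difference in change, and in general they are not that.

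**Working it through.** The plan gives no effect size, SD or LEDD figure on this point, so there is no stated number to reproduce.

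**1. The identity.** For a least-squares fit with the other covariates unchanged:

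total difference = adjusted difference + γ × δ

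Here γ is the fitted LEDD-change slope in the adjusted model, and δ is the group difference in LEDD change given months in trial and baseline Hoehn-Yahr. The two differences agree only if γ = 0 or δ = 0. Section 6 does not define its logarithmic linear model. The identity is exact for least squares on a raw or logged outcome and approximate for a log link. It covers omitting LEDD change. It does not cover adding baseline LEDD.

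**2. Base illustration (every effect input is assumed).** Time T = 3.5 years. Underlying worsening is 4 points/year in controls and 3 with Tai Chi, SD 3. LEDD rises g = 15 mg per point, with noise SD 150 mg. Each mg lowers the ON score by k = 0.02 points.

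- Medication-free difference: (3 − 4) × 3.5 = −3.5
- LEDD gap: δ = 15 × (−3.5) = −52.5 mg
- Total ON difference: −3.5 − 0.02 × (−52.5) = −2.45
- Variance of underlying change: (3 × 3.5)² = 110.25
- Slope of underlying change on LEDD change within group: b = 15 × 110.25 / (15² × 110.25 + 150²) = 1653.75 / 47306.25 = 0.0350
- Adjusted difference: −3.5 − b × (−52.5) = −1.66 (b unrounded)
- Check: γ = b − k = 0.0150, and −1.66 + 0.0150 × (−52.5) = −2.45

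**3. Grid and follow-up length.** The grid has g at 5, 10, 15, 20; k at 0.01, 0.02, 0.03; noise SD at 100, 150, 200, 300 mg: 48 settings.

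The documents conflict on the shortest time in trial. Section 6 has "5th Class: start from Jan. 2018", so Jan 2018 to Nov 2019 is about 22 months. The Overview has classes starting up to Jan 2019, so Jan 2019 to Nov 2019 is about 10 months. The longest, Jan 2016 to Jun 2021, is about 65 months. In the table, MF is the medication-free difference.

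| Time | Adjusted as % of total | Within 20% | Base case, adjusted v total | Adjusted nearer MF than total is |
|---|---|---|---|---|
| 10 months | 100 to 243 | 24 of 48 | −0.78 v −0.58 | 47 of 48 |
| 22 months | 57 to 220 | 31 of 48 | −1.41 v −1.28 | 37 of 48 |
| 3.5 years | 23 to 168 (median 88) | 28 of 48 | −1.66 v −2.45 | 15 of 48 |
| 65 months | 11 to 115 | 16 of 48 | −1.49 v −3.79 | 6 of 48 |

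The trend with time assumes a constant LEDD noise SD. If that SD grew in proportion to time, the percentage would not change.

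**4. Direction.**
- Base inputs at 3.5 years, but no progression effect and LEDD 100 mg lower with Tai Chi for another reason: total 0.02 × 100 = +2.0, adjusted 0.0350 × 100 = +3.5. With LEDD 100 mg higher, both signs reverse.
- A separate simulation of 1,000,000 patients had no group effect on ON change, LEDD 50 mg lower with Tai Chi, and dose following progression. It gave total 0.00 and adjusted +0.74, with γ = 1.49 points per 100 mg (0.74 − 1.49 × 0.50 ≈ 0). Adjustment can therefore create a difference where the total is zero.
- When γ or δ was zero, the two results agreed to within 0.01.

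**The case against.** The plan already contains comparisons that do not condition on LEDD change: t-tests with confidence intervals on propensity-matched groups, LEDD change as its own outcome, and a survival analysis of therapy increase. This stands, and it limits the point. A reader might infer that the primary result is distorted. The documents do not support that. The primary is a yearly rate, the adjusted model is written for change from baseline to each follow-up, and the primary may come from the t-test. The t-test omits months in trial and baseline Hoehn-Yahr, however, and the plan never says which analysis governs.

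It can also be argued that adjusting for medication is sensible when scores are taken ON. This stands in part: at short follow-up in the illustration, the adjusted value is usually the one nearer the medication-free difference. At long follow-up it usually is not. If a same-medication comparison is intended, the plan should say so.

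A reader might further infer that dropping the covariate makes the UPDRS and LEDD evidence separate. It does not. The total ON-state difference also contains the LEDD gap through the drug effect (k × δ in step 2), so the two must be read together under either model.

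Finally, all magnitudes rest on assumed inputs, and many settings show little change. They show what is possible, not what is likely here.

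**Conclusion.** The concern holds in limited form and should be fixed. The only covariate-adjusted rating-scale model conditions on a post-baseline variable that the plan itself treats as an outcome. Its group coefficient equals the total ON-state difference only when γ × δ = 0, and in general it is not a clean medication-free difference. This follows from the text and from least-squares algebra, and it is certain for the adjusted scale results. For the annual UPDRS rate it remains an inference until the primary analysis is named.

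It would be tempting to say that the adjustment understates, or overstates, the Tai Chi effect. The documents support neither. In the illustrations the adjusted value was smaller than the total, larger, or non-zero where the total was zero, and the balance shifted with follow-up length, whose minimum the plan leaves unclear. Because the groups are not randomised, even the total is a group difference and not automatically a causal effect.

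**What to change.** - Remove LEDD change from the main adjusted model for UPDRS total and the other scales. Keep treatment group, months in trial, baseline Hoehn-Yahr, and education for PDCRS.
- Baseline LEDD may be added as a separate, optional adjustment for baseline imbalance, since matching does not cover it. It is not needed to reach the total difference.
- Name the primary analysis of the annual UPDRS rate, either this model or the t-test on matched groups, and state the difference it estimates.
- Report LEDD change beside the UPDRS result.
- Keep the present model as a labelled sensitivity analysis, described as comparing patients with the same LEDD change.
- Reconcile the last class start date between the Overview and section 6.

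The cost is one covariate removed, a few sentences and a re-run. No new data are needed, because baseline LEDD is already required to compute LEDD change. ON-state drug masking and confounding from the non-randomised comparison remain. The plan is written in the past tense, so if results are already known the change should be labelled post hoc.

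### With 1000 bootstrap resamples and an undefined Bonferroni correction, a result close to the threshold can change with the random seed

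*Combined protocol and SAP*

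**What the plan says.** The p-value method is in section 6 (Statistical Analysis), after the description of the covariance model. It is a p "value with the bootstrap method for resampling 1000 times". The same paragraph says "mean change with its 95% confidential intervals (CIs) was introduced" and that "Bonferroni correction was introduced". Nothing further is given on the alpha, the tests that share the correction, the divisor, how a p value is formed from the resamples, or the seed.

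Other sections bear on how many tests there could be:

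- Section 5.1: "The primary outcome was the annual change of UPDRS total score", measured at three follow-ups.
- Section 6: the model is applied to "Analyses of the adjusted means of change from baseline to each follow-up in rating scales", which suggests up to three tests per scale.
- Section 5.2 lists "Motor evaluations: UPDRS part III as overall motor evaluations; TUG and BBS" and "Other non-motor symptoms, including autonomic function, mood, sleep and cognition, assessed by rating scales", plus quality of life, LEDD, complications and a survival outcome.
- The note in section 5.2, introduced by "We consider the following aspects as the evidences for delaying disease progression", names three endpoints.

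**The concern.** A bootstrap p value is itself an estimate, with random error that depends on the number of resamples. Bonferroni lowers the threshold, and for a fixed number of resamples the relative error of p grows as p falls. The plan fixes the number of resamples without fixing the threshold it must serve.

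At stake is reproducibility. If the p value for the primary outcome falls near its threshold, two analysts running the same code on the same data with different seeds could reach opposite conclusions. With no seed specified in advance, a reader also cannot exclude that one run was preferred to another. For the secondary outcomes the error is larger if the correction spans many scales and visits.

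**Working it through.** The plan states no threshold or precision target, so there is no figure of its own to reproduce.

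**Inputs**
- B = 1000 resamples (section 6).
- Alpha = 0.05, two-sided. Assumed; suggested only by the 95% intervals.
- p = (b+1)/(B+1), where b counts resamples at least as extreme as the observed result. Assumed; the plan gives no formula.
- m = number of tests in the Bonferroni family. Not stated, so shown over a range. For the primary outcome, m = 1 (a single annual rate) or m = 3 (one test per follow-up).
- *True p* means the value that unlimited resamples would give.

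**Step 1: Monte Carlo error at the threshold.** SE = sqrt(a(1−a)/B), with a = 0.05/m.

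| m | a | SE at B = 1000 | SE/a |
|---|---|---|---|
| 1 | 0.05 | sqrt(0.05 × 0.95/1000) = 0.0069 | 14% |
| 3 | 0.0167 | sqrt(0.0167 × 0.9833/1000) = 0.0040 | 24% |
| 15 | 0.00333 | 0.0018 | 55% |
| 45 | 0.00111 | 0.00105 | 95% |

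The row m = 15 is the 14 measures that can be counted from sections 4 and 5.2 (UPDRS total, UPDRS III, TUG, BBS, nine non-motor scales and PDQ-39), plus LEDD, at one visit. The row m = 45 is the same set at three visits.

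**Step 2: chance of a wrong call, m = 3.** Significance needs (b+1)/1001 ≤ 0.0167. Since 16/1001 = 0.0160 and 17/1001 = 0.0170, this means b ≤ 15. With b ~ Binomial(1000, true p):

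| True p | Called significant | Wrong call |
|---|---|---|
| 0.010 | 95% | 5% |
| 0.014 | 67% | 33% |
| 0.020 | 15% | 15% |
| 0.025 | 2% | 2% |

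**Step 3: the same with no correction, m = 1.** Significance needs b ≤ 49. A true p of 0.045 is missed in 24% of runs and 0.055 passes in 23%. True values of 0.03 and 0.07 are called correctly in over 99%.

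**Step 4: can the threshold be reached?** The smallest attainable p is 1/1001 = 0.0010 for a two-sided count, or 2/1001 = 0.0020 if a tail proportion is doubled.
- Two-sided count: 0.05/50 = 0.00100 is reachable; 0.05/51 = 0.00098 is not.
- Doubled tail: 0.05/25 = 0.0020 is reachable; 0.05/26 = 0.0019 is not.
- At m = 45 a two-sided count can pass, but only with b = 0. A true p at half that threshold would then be called significant in 57% of runs.

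**Step 5: more resamples.**
- At m = 3, SE/a falls to 7.7% with B = 10,000. With B = 20,000, a true p of 0.014 is missed in 0.1% of runs and 0.020 passes in 0.02%.
- A relative SE of 10% needs B = (1−a)/(0.01a): about 1,900 at m = 1, 5,900 at m = 3, 29,900 at m = 15 and 89,900 at m = 45.

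**The case against.** The strongest reply is that the plan states no threshold for 1000 resamples to be too coarse for. The values 0.0167 and 0.00111 are constructions, and the real gap is the undefined family, alpha and p-value formula. This stands, and is why every threshold above is conditional. It does not remove the point: at a plain 0.05 the error rates near the line are still 24% and 23%.

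A second reply is that the effect is narrow, and that every Monte Carlo p value is uncertain close to its cut-off. This also stands. It limits the size of the point, but the uncertain zone can be made much narrower at almost no cost.

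A third is that the figures depend on the formula. With b/B, a true p of 0.014 is missed in 24% of runs rather than 33%, and the smallest p is zero. With a bootstrap SE and a normal reference there is no floor, and the Monte Carlo error of the SE is about 1/sqrt(2 × 1000) = 2.2%. The plan is compatible with each of these, so it should say which is meant.

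A reader might go further and infer that no secondary outcome could ever reach significance. One could count 15 outcomes at three visits (45), six complications at three visits (18) and one survival outcome, giving 64 tests and a threshold of 0.05/64 = 0.00078, below 0.0010. The documents do not support this. They do not say that these tests form one family, that complications are tested at every visit, or that complications and the survival outcome are bootstrapped. LEDD change is a covariate in the model for the rating scales, so its place among the model outcomes is itself doubtful. At 45 tests a two-sided count can still pass.

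**Conclusion.** The point holds in a limited form. Given alpha 0.05 and a counting p value, 1000 resamples leave a Monte Carlo SE of 14% of the threshold at 0.05 and 24% at 0.0167. A primary result near the line could therefore be decided by the seed. Results well away from it are safe: at 0.0167, true p values of 0.010 or lower, or 0.025 or higher, are called correctly in at least 95% of runs.

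An unreachable threshold is a conditional risk only. It needs one family of more than about 50 tests with a two-sided count, or more than 25 with a doubled tail, together with a formula that has a floor. The documents establish none of these conditions. This is an inexpensive improvement to a number that the plan does state, and does not show that the analysis is invalid.

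**What to change.** In section 6:

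1. Replace 1000 with at least 10,000 resamples. Using 20,000 brings both example errors at 0.0167 to about 0.1% or less.
2. Fix the seed in advance and record it. A seed alone makes the answer repeatable but no more precise, so it does not replace item 1.
3. State the p-value formula as (b+1)/(B+1), and whether the count is two-sided or a doubled tail.
4. State the alpha, the tests in the Bonferroni family and the divisor, including whether the primary outcome counts as one test or three.
5. If the family is near 45 tests, use about 100,000 resamples (relative SE about 10%) or a model-based p value for those outcomes.

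The cost is a few sentences in the plan and computing time. No data collection or patient procedure changes.
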